7.9.4.4.1. Joint Function

The HJHS is a validated outcome tool developed for the assessment of joint health in people with hemophilia.⁵¹ HJHS measures joint health in the domain of body structure and function (i.e., impairment) of the six joints most commonly affected by bleeding in hemophilia: the left and right knees, left and right ankles, and left and right elbows. It also measures the participant's global gait score. Scores range from 0 to 124 points. This physical examination assessment tool conducted by a healthcare provider is sensitive enough to pick up the subtle early signs of joint damage and is appropriate for monitoring joint change over time or assessing efficacy of treatment regimens among participants receiving both prophylactic and on-demand therapy.⁵² Scores within each of the six joint categories will be summed, if not already summed in the DHR. The summed joint scores and the global gait score are expected to be captured at baseline, and at each follow-up time point (every 6 months for approximately 3 years). Participants who have a baseline and at least one follow-up measure for HJHS outcomes will be included in the analysis. To determine the completeness rate, the number of participants in each Cohort with a recorded HJHS score (joint scores and/or global gait score) at a given timepoint will be divided by the total number of participants eligible within that Cohort (i.e., have enough follow-up time). More specifically, a minimum and full compliance rate will also be calculated. The minimum completion rates are defined as the number of participants who have the baseline measure and at least one post-baseline measure (to be calculated at all timepoints of interest including 12-months, 24-months and 36-months), divided by the total number of enrolled participants. The full completion rate is defined as number of participants who have the baseline measure and all post-baseline measures, divided by the total number of enrolled participants.

The analytical techniques described in Section 7.9.4.4 will be applied to the HJHS outcomes including descriptive statistics, change from baseline analyses, repeated measures model analyses, and responder analyses. Please refer to Section 7.9.4.4 for details.

7.9.4.4.2. Haemo-QoL-A Score

The Haemo-QoL-A questionnaire is a validated hemophilia-specific health-related quality of life questionnaire for adults.⁵³ It consists of 41 questions covering six domains (physical functioning, role functioning, worry, consequences of bleeding, emotional impact, and treatment concerns). Items are answered by participants on a 6-point Likert scale, ranging from 0 (none of the time) to 5 (all of the time). Higher scores indicate better health related QoL or less impairment for that particular measure. See Annex 12.2 for the scoring guide. Transformed scores will be calculated for each domain by summing the individual item scores for each domain (actual raw total score), dividing it by the possible raw score range, and then transforming to a standardized scale ranging from 0-100.⁵⁴ The formula for the transformed scale is shown below:

$$\text{Transformed score} = \frac{\text{actual raw total score}}{\text{possible raw score range}} \times 100$$

Scores for each of the six domains and for the total score are expected to be captured at baseline, and at each follow-up time point (every 6 months for approximately 3 years). Participants who have a baseline and at least one follow-up measure for Haemo-QoL-A outcomes will be included in the analysis. To determine the completeness rate, the number of participants in each Cohort with a recorded Haemo-QoL-A score (six domains and/or total score) at a given timepoint will be divided by the total number of participants eligible within that Cohort (i.e., have enough follow-up time). More specifically, a minimum and full compliance rate will also be calculated. The minimum completion rate is defined as the number of participants who have the baseline measure and at least one post-baseline measure (to be calculated at all timepoints of interest, including 6-months, 12-months, 18-months, 24-months, 30-months, and 36-months), divided by the total number of enrolled participants. The full completion rate is defined as number of participants who have the baseline measure and all post-baseline measures, divided by the total number of enrolled participants.

The analytical techniques described in Section 7.9.4.4 will be applied to the Haemo-QoL-A outcomes including descriptive statistics, change from baseline analyses, repeated measures model analyses, and responder analyses. Please refer to Section 7.9.4.4 for details.

7.9.4.4.3. Pain Score

The BPI-sf is a validated and frequently used patient-reported questionnaire that assesses pain severity and the impact of pain on daily functions (i.e., pain interference).⁵⁵ The BPI-SF measures generic pain (i.e., is not indication-specific) has been used and validated in hemophilia.⁵⁶⁻⁵⁸

Four questions measure pain intensity (worst pain, least pain, average pain, and pain now). The pain intensity items use an 11-point numerical scale with zero signifying (“no pain”) and 10 signifying (“pain as bad as you can imagine”). The pain interference scale assesses the degree to which pain interferes with 7 constructs (General activity, Mood, Walking ability, Normal work, Relation with people, Sleep, and Enjoyment of life). The pain interference items use an 11-point numerical scale with zero signifying “does not interfere” and 10 signifying “completely interferes.” Both the pain intensity and pain interference items have a recall period of the “last/past 24 hours”. Four other items allow patients to report on “the nature of their pain.” Scores are expected to be reported for pain intensity and pain interference at baseline, and at each follow-up time point (every 6 months for approximately 3 years). Participants who have a baseline and at least one follow-up measure for BPI-sf outcomes will be included in the analysis. To determine the completeness rate, the number of participants in each Cohort with a recorded BPI-sf score (average pain and/or pain intensity) at a given timepoint will be divided by the total number of participants eligible within that Cohort (i.e., have enough follow-up time). More specifically, a minimum and full compliance rate will also be calculated. The minimum completion rate is defined as the number of participants who have the baseline measure and at least one post-baseline measure (to be calculated at all timepoints of interest, including 6-months, 12-months, 18-months, 24-months, 30-months, and 36-months), divided by the total number of enrolled participants. The full completion rate is defined as number of participants who have the baseline measure and all post-baseline measures, divided by the total number of enrolled participants.

The analytical techniques described in Section 7.9.4.4 will be applied to the BPI-sf outcomes including descriptive statistics, change from baseline analyses, repeated measures model analyses, and responder analyses. Please refer to Section 7.9.4.4 for details.

7.9.4.5. Safety Events

Population	Measurement Period	Analysis Notes
All participants	All available follow-up data	
Safety events will be compared between the Roctavian and SoC Cohorts
 
Due to the possibility of unknown responses, there may be insufficient data to fully describe participant comorbidities that may confound the 'true' causal reason for an event.

Safety events outlined in Table 5 will be reported for both the Roctavian and SoC Cohorts.

Regarding the treatment policy estimand data analysis, the proportion of participants with each event will be calculated from index through the full follow-up period, without considering any intercurrent events. Given safety outcomes are event-based, for safety outcomes occur multiple times over the follow-up period (e.g., thromboembolic events), IPTW-weighted negative binomial regression models will be fit to compare safety outcomes between Roctavian and SoC Cohorts. For safety outcomes expected to occur once (e.g., death), IPTW-weighted log binomial regression models will be fit to compare safety outcomes between Roctavian and SoC Cohorts.

IPTW will be applied to create more similar Roctavian and SoC Cohorts. Other clinically significant prognostic factors or covariates that remain imbalanced after propensity score adjustment will be included in the model as well. Regression coefficients, corresponding 95% CIs and p-values will be reported for all explanatory variables included in the model. In the case that there are little to no events $n < 10$, that the relative risk log-binomial regression or negative binomial regression estimates are not stable, a logistic regression (which can approximate relative risk in a rare outcome⁵⁹) with firch correction will be conducted.

Under the hypothetical estimand data analysis, the event rate and incidence rate of each event will be calculated from index through the full follow-up period, where all participants will be included in analyses of event or incidence rates. Further, to compare Roctavian and SoC Cohorts safety outcomes under the hypothetical estimand, IPTW-weighted incident rate ratios (IRRs) will be estimated at the incident/event rate among the Roctavian Cohort divided by the incident/event rate among the SoC Cohort. See below for the event and incidence rate calculations:

- Event rates will be calculated as the number of events per 100 person-years: (number of events in each Cohort during the overall follow-up period / total number of days in each Cohort during the follow-up period) * 365.25 * 100. Event rates will be calculated for events that may happen multiple times per person.
- Incidence rate will be calculated as the number of new events (first occurrence of event) per 100 person-years: (number of new events in each Cohort during the overall follow-up period / total number of days in each Cohort during the follow-up period) * 365.25 * 100. Incidence rates will be calculated for events that can only happen once per person.

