
For safety outcomes, PS may be less likely to control for potential confounding due to the expected rarity of the safety events of interests. The risk of spurious findings for the safety comparisons are particularly notable for 'all-cause' outcomes that do not consider relationship to hemophilia treatment as characteristics of the cohort. For example, if one cohort is older, events due to unrelated causes (ie, risks associated with older age) could be misinterpreted to be associated with a product.

The data utilized for this analysis will be collected in the DHR. The DHR has the advantage of being an existing system with which German physicians are familiar and should minimize site burden for additional data collection specific to the AbD, though the DHR is more similar to a secondary data source for the purposes of this analysis. Due to the anonymized nature of the DHR, the DHR will be treated as the source data for the purposes of source data

verification (see Section 11.8). Data fields in the DHR were reviewed in the design of this study and additional data fields were requested to be added as needed. Despite these considerations in the design of the study, the administration of the DHR is not controlled by the study sponsor and therefore the potential for missing data and/or implausible data values are possible. Data monitoring activities (described in Section 11.8) are anticipated to minimize missing data and implausible values in the final data set, though data for interim analyses may be more prone to potential missing/erroneous data. As missing/erroneous data are possible, the extent of missing data (or data excluded due to implausible values) will be quantified (when applicable). Imputation for missing data may be considered based on the patterns of missingness and effect of missing data on the interpretability of the results. Further detail regarding missing data procedures will be documented in the SAP.

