7.3.4. Study Population

The study population will include male PwSHA without a history of (or current) inhibitors to FVIII in Germany. Participants will be identified from the DHR (see Section 7.5.1 for further description of the DHR) and are expected to provide written informed consent to be included in this study. Participants will be captured in either the Roctavian or SoC Cohorts based on the treatment they receive during the study recruitment window. The study aims to enroll at least 67 PwSHA into the Roctavian Cohort and at least 330 PwSHA into the SoC Cohort. The therapeutic treatment strategy for an individual who consents to this study is made independently of the decision to participate in the study and enrollment into this study will not inform the treatment strategy.

Participants will be selected into one of two mutually exclusive Cohorts based on the treatment they receive for HA. The Roctavian Cohort will include participants who received Roctavian during the recruitment period. The index date for these participants will be the date Roctavian is administered. The SoC Cohort will include participants who received prophylactic treatment with any of the following SoC treatments, recombinant or human plasma-derived (PD) blood coagulation FVIII or emicizumab. Participants in the SoC Cohort cannot have a history of exposure to Roctavian. Eligibility criteria will be confirmed at time of enrollment based on DHR field that the participant fulfills the AbD inclusion/exclusion criteria.

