7.6. Study Sample Size

The primary goal of HA treatment is to reduce the bleeding rate or to achieve freedom from bleeding. As an approximation of the appropriate number of cases for the data collection accompanying the application, the Institute for Quality and Efficiency in Health Care (IQWiG) conducted the sample size calculation based on ABR for treated bleeds. Evaluation of the ABR is performed using a negative binomial model.

The formula for The sample size calculation is as follows:

$$N_1 \geq \frac{(z_\alpha \sqrt{V_0} + z_\beta \sqrt{V_1})^2}{(\log(R_0) - \log(\lambda_2/\lambda_1))^2}$$

$$N_2 = \theta N_1$$

Where:

$$V_1 = \frac{1}{\mu_t} \left(\frac{1}{\lambda_1} + \frac{1}{\theta \lambda_2} \right) + \frac{(1 + \theta)\varphi}{\theta}$$

V_0 is computed using the fixed marginal total method, the 2nd method recommended by Zhu et al.:²⁷

$$V_{02} = \frac{(1 + R_0\theta)^2}{\mu_t R_0 \theta (\lambda_1 + \theta \lambda_2)} + \frac{(1 + \theta)\varphi}{\theta}$$

N_1 is the sample size for control, N_2 is the sample size for intervention. $\theta = \frac{N_2}{N_1}$, which is the sample size ratio; R_0 is the superiority margin ratio at the null hypothesis. In this case, R_0 is <1 since higher rates are worse. λ_1 is the event rate in the control group, and λ_2 is the event rate in the intervention group. φ is the dispersion parameter, and μ_t is the average exposure time. z_α is the z-score at the significance level, z_β is the z-score at the power value.

When higher rates are worse, the superiority by a margin test hypotheses are

$$H_0: \frac{\lambda_2}{\lambda_1} \geq R_0 \quad \text{vs.} \quad H_1: \frac{\lambda_2}{\lambda_1} < R_0$$

Where $R_0 < 1$.

The relative effect measure is the incidence rate ratio of Roctavian over SoC, which can be tested against the shifted null hypothesis of 0.5, assuming a significance level $\alpha = 2.5\%$ with a one-sided test, and power of at least 80%. Higher values for the ABR (parameter λ) stand for a worse outcome. Furthermore, a distribution of the Sample Roctavian vs. SoC of 1:5 is assumed (sample size ratio $\theta = 0.2$). Other required parameters are the Average Exposure Time ($u_t = 1$ year), the ABR for the SoC and Roctavian groups ($\lambda_{SoC} = 3$, $\lambda_{Roctavian} = 0.85$) and a value for the overdispersion ($\phi = 1.5$). This results in a total sample size of at least 397 participants (Roctavian Cohort $n = 67$, control Cohort $n = 330$).

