7.8.3.1. Inverse Probability of Treatment Weighting

IPTW will be implemented to create a baseline reference of propensity score weights for comparison. Using this approach, each participant is assigned a weight representing the inverse probability of being assigned to their respective group. Thus, IPTW aims at giving more importance (i.e., more “weight”) to those participants that have unexpected propensity score values. For the treated group

(Roctavian Cohort), the weight, W , assigned in the IPTW method for each individual, i , based on propensity score, P_i , is:

$$W_i = \frac{1}{P_i}$$

For the control group (SoC Cohort), participants receive weights of:

$$W_i = \frac{1}{(1 - P_i)}$$

As the characteristics of the population that will be treated with Roctavian are unknown at the time of the SAP being drafted, it is possible that large differences in characteristics between the Roctavian and SoC Cohorts will exist. If this is the case, some participants may have extreme propensity score weights and, though representing a small portion of the observed population, have a disproportionate influence on the analysis. This outsized influence of individuals with extreme weights may increase variance and confidence intervals of the ATE estimate.³⁸

Stabilized weights can be used instead of the original, unstabilized weights. To calculate the stabilized weights, the numerator of the unstabilized weights is replaced by the marginal probability of receiving Roctavian and SoC in the overall sample. Additionally, weight values greater than five will be truncated to five due to the potential bias of outliers.^{39, 40}

For the Roctavian Cohort, the stabilized weight, W , assigned in the IPTW method for each individual i , is obtained by dividing the marginal probability of receiving Roctavian (i.e., a propensity score without considering covariates) P_T by individual's propensity score, P_i :

$$W_i = \frac{P_T}{P_i}$$

For the SoC Cohort, participants receive weights of:

$$W_i = \frac{(1 - P_T)}{(1 - P_i)}$$

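### The Firth fallback for sparse safety outcomes has no rule for zero events and no stated weighting, so at zero or near-zero counts its odds ratio reflects cohort sizes and weights rather than data

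*Protocol*

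**What the plan says.** For the treatment policy estimand, SAP section 7.9.4.5 compares safety outcomes by weighted negative binomial regression (events that can recur) or weighted log-binomial regression (events that occur once). The fallback opens with "In the case that there are little to no events", sets the threshold at fewer than 10, and continues: "log-binomial regression or negative binomial regression estimates are not stable, a logistic regression (which can approximate relative risk in a rare outcome"). A Firth correction is applied. Coefficients, 95% intervals and p-values are to be reported from the models. No minimum number of events is set.

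Three other parts of the documents bear on this:

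- **Cohort sizes.** SAP section 7.6 states that "a distribution of the Sample Roctavian vs. SoC of 1:5 is assumed", and SAP section 7.3.4 that "The study aims to enroll at least 67 PwSHA into the Roctavian Cohort and at least 330 PwSHA into the SoC Cohort".
- **Weights.** SAP section 7.9 says in general that models carry the propensity weights. The base formula in SAP section 7.8.3.1 (and protocol section 10.3.5) is the plain inverse probability. The SAP then adds: "Stabilized weights can be used instead of the original, unstabilized weights". Weights above five are cut to five. Section 7.9.4.5 does not say which form the fallback uses.
- **Expected frequency.** Protocol section 10.5 says of safety outcomes that "PS may be less likely to control for potential confounding due to the expected rarity of the safety events of interests". No rates are given.

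**The concern.** Firth's penalty keeps estimates finite when a cohort has no events. In a model with a single cohort term it does so by adding the same half event to each cohort, whatever its size. Half an event among 67 people is a risk about five times that of half an event among 330. When there are almost no real events, the printed odds ratio mainly reflects the size ratio, or the ratio of weighted sizes.

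The outcomes likely to reach this rule include deaths, thromboembolic events, malignancies, inhibitors and severe liver disease. A report could then carry a ratio that looks like harm or like benefit, depending on a weighting choice the text leaves open, when the data contain no comparative information.

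**Working it through.** **Inputs.** Cohort sizes 67 and 330 (SAP sections 7.3.4 and 7.6), fallback rule (SAP section 7.9.4.5), weight formulas and truncation at five (SAP section 7.8.3.1). The documents give no safety event rates, so any risk used below is an assumption.

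**Cohort sizes reproduced.** With the SAP's formula:

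- V0 = 1.1²/(0.5 × 0.2 × (3 + 0.17)) + 1.2 × 1.5/0.2 = 12.817
- V1 = 1/3 + 1/(0.2 × 0.85) + 9 = 15.216
- N1 = (1.960√12.817 + 0.842√15.216)²/(ln 0.5 − ln(0.85/3))² = 328.8, so 329, and 0.2 × 329 gives 66

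The total of 395 agrees closely with the plan: "This results in a total sample size of at least 397 participants".

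**Firth odds ratio.** With a cohort term only, for a events of n1 and c events of n2:

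OR = [(a + 0.5)/(n1 − a + 0.5)] / [(c + 0.5)/(n2 − c + 0.5)]

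Iterative fitting of the penalised likelihood gave the same values. Unweighted, 67 versus 330:

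| Events, Roctavian vs SoC | Calculation | OR | Profile 95% CI | p |
|---|---|---|---|---|
| 0 vs 0 | (0.5/67.5)/(0.5/330.5) | 4.90 | 0.03 to 907 | 0.45 |
| 0 vs 1 | (0.5/67.5)/(1.5/329.5) | 1.63 | 0.01 to 31 | 0.78 |
| 0 vs 2 | (0.5/67.5)/(2.5/328.5) | 0.97 | 0.01 to 12 | 0.99 |
| 0 vs 3 | (0.5/67.5)/(3.5/327.5) | 0.69 | 0.01 to 7.3 | 0.80 |

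With 70 in the Roctavian Cohort the first two become 4.69 and 1.56.

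**Effect of the weight form on the first two tables.**

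| Weights | Weighted sizes | 0 vs 0 | 0 vs 1 |
|---|---|---|---|
| None | 67, 330 | 4.90 | 1.63 |
| Stabilised (two simulated weight sets) | 67, 330 | 4.90 | 1.60 to 1.76 |
| 1/P, untruncated, average weights 397/67 and 397/330 | 397, 397 | 1.00 | 0.29 |
| 1/P, Roctavian weights cut to five | 335, 397 | 1.18 | 0.35 |

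For example, the 0.29 is (0.5/397.5)/(1.703/396.3), because one SoC event carries weight 397/330 = 1.203.

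**How often these tables would arise (assumed equal true risk of 1% in both cohorts).**

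- 0 vs 0: 0.99³⁹⁷ = 1.9%
- 0 vs 1: 330 × 0.01 × 0.99³⁹⁶ = 6.2%, so the two together about 8.0%
- 0 vs 2 or more, where the OR is below 1: 0.99⁶⁷ − 0.080 = 43%

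Rarer outcomes shift this. If the unweighted Firth model were used for every total under 10, the geometric mean OR under equal risk would be 3.8 at a risk of 0.1%, 2.0 at 0.5%, 1.4 at 1% and 1.1 at 2%.

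**Exact limits for no events.** Upper 97.5% limit = 1 − 0.025^(1/n): 5.4% for 0/67 and 1.1% for 0/330.

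**The case against.** The strongest reply is that the effect is conditional and the report would not mislead a careful reader.

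- **Weights.** A reader might infer that the plan will report an odds ratio of 4.9 whenever nobody has an event. The documents do not support that. The general rule is that models are weighted, and the base weight is 1/P, which gives 1.00 and 0.29. The higher figures belong to unweighted or stabilised fits. This stands, and it leaves the dependence on an unstated choice as the defect.
- **Trigger.** The fallback requires unstable estimates as well as a low count. If instability means an empty cohort (an assumption), that occurs in about 53% of studies at 1% risk: 0.99⁶⁷ + 0.99³³⁰ − 0.99³⁹⁷. It is therefore wrong to treat every outcome with fewer than 10 events as reaching Firth. This also stands, but both headline tables have an empty cohort and do reach it.
- **No false conclusion.** The intervals would be printed, secondary p-values are nominal under SAP section 7.9, and no decision rule uses them. This stands.
- **Existing reporting.** Protocol section 3.3 makes safety comparison conditional on its being warranted. The SAP's Table 15 shell shows counts and percentages, and rates per person-time are planned. This answers most of any complaint that follow-up time is lost.
- **Firth itself.** It is a standard remedy for separation. Replacing it by an unadjusted comparison would give up confounding control in a non-randomised study, and protocol section 10.5 warns about age differences. This stands against abandoning Firth for 1 to 9 events.

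**Conclusion.** The point holds in limited form. As written, the rule can produce an odds ratio, interval and p-value, to be read as an approximate relative risk, from a table with no events. At 67 versus 330 that ratio is 4.90 or 1.00, depending on whether the fit is unweighted or stabilised, or uses untruncated 1/P weights. With one SoC event it is 1.63 or 0.29. The same data can thus point in opposite directions.

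A reader might go further and infer a built-in false signal of harm. That does not follow: the intervals span orders of magnitude, neither result is significant, and the unweighted ratio drops below 1 once the SoC Cohort has two or more events and the Roctavian Cohort none. The fault is an uninformative, weight-dependent point estimate at zero or near-zero counts.

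The figures assume a cohort term only. SAP section 7.9.4.5 also allows imbalanced covariates in the models, which would change them. The frequencies rest on assumed event risks.

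**What to change.** Amend the fallback in SAP section 7.9.4.5 in three respects:

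1. When neither cohort has an event, report no ratio and no p-value. Give 0/n per cohort with the exact 97.5% upper limit (5.4% for 0/67, 1.1% for 0/330).
2. State in advance which weight form the Firth model uses, including truncation.
3. For 1 to 9 events in total, keep the Firth estimate but print crude counts, person-years and an exact rate ratio interval, labelled unadjusted, beside it. Do not interpret the Firth odds ratio as a relative risk when either cohort has no event.

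The cost is a paragraph of SAP text, slightly more reporting, and the loss of a model-based ratio for outcomes with no events, where it carries no information.

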Descriptive statistics will be used to summarize the absolute and change from baseline at the time of an assessment for the total and domain scores for the Haemo-QoL-A and the BPI-SF. For the BPI-SF the pain interference and pain intensity scores will be taken as the domains. A repeated measurement analysis model will be used to compare the changes in scores between the treatment groups. Participants with an evaluable baseline score and at least one evaluable post-baseline score will be required for the specific analysis be included in the change from baseline analyses.

In addition, responder analyses will be considered for improvement and deterioration for the BPI-SF pain interference and pain intensity scales. The BPI-SF pain intensity score will be defined as the Question 5 “average pain”. The BPI-SF pain interference score will be defined as the average to all 7 subitems of Question 9 (9A to 9G).

All analysis details and scoring methods will be described in the SAP. It is expected that no missing data will be imputed.

All PROs comparisons will be interpreted after 3 years of follow-up, or latest available follow-up score if a full 3 years of follow-up is not available.

10.3.7.5. Objective: To compare safety events of interest.

Safety events outlined in [Table 8](#) will be described in each cohort. Summaries of the proportion, event rate, and incidence rate of each of the safety events among all participants by cohort will be provided. Safety events will be described from index through follow-up. All participants will be included in analyses of event and incidence rates, while analyses of the proportion of participants will only include those participants with follow-up for the full time over which the proportion is calculated. Safety outcomes will be compared as relative risks based on the incidence of an event for analyses of the treatment policy estimand and as incidence rate ratios censoring a participants person time at the time of the event for analyses of the hypothetical estimand.

10.3.7.6. Objective: To describe time to resumption of prophylactic treatment among participants administered Roctavian

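### Under the hypothetical estimand, the SAP divides first safety events by all follow-up days, whereas the protocol stops person-time at the event. Non-fatal first-event rates come out slightly low and their ratios are distorted.

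*Protocol*

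**What the plan says.** Protocol section 10.3.7.5 asks for the proportion, event rate and incidence rate of each safety event. Under the hypothetical estimand it compares the cohorts by "incidence rate ratios censoring a participants person time at the time of the event for analyses of the hypothetical estimand".

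SAP section 7.9.4.5 covers the same comparison. It says that "the event rate and incidence rate of each event will be calculated from index through the full follow-up period", and that the ratio is the "incident/event rate among the Roctavian Cohort divided by the incident/event rate among the SoC Cohort". Two definitions follow:

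- **Event rate**, for outcomes that may recur: all events over the cohort's total follow-up days.
- **Incidence rate**: "number of new events (first occurrence of event) per 100 person-years", computed as "number of new events in each Cohort during the overall follow-up period / total number of days in each Cohort during the follow-up period". The denominator is worded exactly as for the event rate. The definition closes with a limit on scope: "Incidence rates will be calculated for events that can only happen once per person".

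SAP section 7.3.3.1 lists what ends a participant's follow-up. Death is on the list. A first inhibitor, malignancy or severe liver event is not, and the additional hypothetical-estimand censoring in SAP sections 7.2.3 and 7.3.3.2 does not add them.

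**The concern.** A participant who has had a first event is no longer at risk of a first event. The SAP counts only the first event in the numerator but leaves the later days in the denominator, so the quotient is not the rate among those at risk. The protocol's rule avoids this. The two sections therefore give different formulas for one planned comparison, and the SAP version is the explicit one that a programmer would be likely to follow.

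At stake are the first-event rates in each cohort, and their ratio, for the non-fatal targeted safety outcomes under one of the two estimands.

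**Working it through.** The documents state no safety rate or ratio, so there is no figure of theirs to reproduce. The hazards below are assumptions, shown as a range.

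**Inputs.** Planned follow-up T = 3 years (SAP 7.3.3). Cohorts of about 70 Roctavian and 330 SoC participants (protocol synopsis). Constant hazard h, no other losses.

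**Formulas.** With person-time censored at the event, the rate estimates h. With the SAP denominator, a non-fatal first-event rate is (1 − exp(−hT))/T. The SAP ratio is the quotient of two such terms.

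**Equal follow-up of 3 years, true ratio 2.0.** All rates are per 100 person-years.

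| True SoC rate | SAP SoC rate | SoC shortfall | True Roctavian rate | SAP Roctavian rate | SAP ratio |
|---|---|---|---|---|---|
| 0.5 | 0.496 | 0.7% | 1 | 0.985 | 1.985 |
| 1 | 0.985 | 1.5% | 2 | 1.941 | 1.970 |
| 2 | 1.941 | 3% | 4 | 3.769 | 1.942 |
| 5 | 4.643 | 7% | 10 | 8.639 | 1.861 |
| 10 | 8.639 | 14% | 20 | 15.040 | 1.741 |

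Worked line for 2 per 100: (1 − exp(−0.06))/3 = 0.01941, that is 1.941 per 100. The pull toward 1 also occurs from below: a true ratio of 0.5 at an SoC rate of 1 per 100 reads 0.504.

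**Unequal follow-up.** SAP section 7.2.3 censors the Roctavian Cohort at resumption of prophylaxis, so its follow-up can be shorter. Assume 1.5 years for Roctavian and 3 years for SoC:

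| True rates, Roctavian vs SoC (per 100 person-years) | True ratio | SAP ratio |
|---|---|---|
| 2 vs 2 | 1.00 | 1.015 |
| 5 vs 5 | 1.00 | 1.037 |
| 5 vs 4 | 1.25 | 1.278 |
| 2 vs 1 | 2.00 | 2.000 |
| 1 vs 2 | 0.50 | 0.511 |

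The first three move away from 1, the fourth is unchanged, and the last moves toward 1. The direction depends on the rates and the follow-up lengths.

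**In counts.** Assume everyone is followed for 3 years and events fall at 1.5 years. This gives 70 × 3 = 210 and 330 × 3 = 990 person-years.

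- 3 vs 5 first events: SAP ratio (3/210)/(5/990) = 2.83; at-risk ratio (3/205.5)/(5/982.5) = 2.87.
- 7 vs 10 first events: SAP ratio (7/210)/(10/990) = 3.30; at-risk ratio (7/199.5)/(10/975) = 3.42.

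**Death.** Follow-up stops at death, so total days already end at the event. Rate and ratio are unchanged.

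**The case against.** The case on the other side limits the point considerably.

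- **Scope.** The SAP restricts incidence rates to once-only events, and the once-only safety outcome it names as an example is death, for which its formula is right. This stands for death. It does not rescue inhibitors, malignancy or severe liver disease if these are counted by first occurrence.
- **Rarity.** Protocol section 10.5 expects the safety events to be rare, and SAP section 7.9.4.5 provides for fewer than ten events. At 0.5 to 2 per 100 person-years the rate error is 3% or less, and with about 70 Roctavian participants the sampling error would be much larger. This stands.
- **Reach.** The treatment-policy comparison, which the G-BA required, does not use these rates, and SAP section 7.9 treats p-values for secondary outcomes as nominal. This stands.
- **Status.** Protocol section 10.3 describes the SAP as a draft to be finalized before the first data cut, so the wording can still be corrected. This bears on cost, not on whether the text is wrong.

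A reader might infer three stronger things that the documents do not support:

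- That all safety rates are too low. Deaths are not affected.
- That the ratios always shrink toward 1. This needs similar follow-up in the two cohorts, which censoring at resumed prophylaxis can break.
- That a frequent outcome such as events leading to hospitalization is materially biased. These can recur, so under the SAP's closing limit they would receive an event rate, for which total days are the right denominator. The references in protocol 10.3.7.5 and earlier in SAP 7.9.4.5 to an incidence rate for each event make this unclear, but they do not show that the faulty formula applies.

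**Conclusion.** The protocol and the SAP contradict each other on the denominator for the same hypothetical-estimand ratio, and the SAP formula is wrong for non-fatal outcomes counted by first occurrence. That FVIII inhibitors, malignancy and severe liver disease fall in this class is a reading: the SAP does not list its once-only outcomes beyond the example of death.

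Under a constant hazard and 3 years of follow-up, the understatement is about 0.7 to 3% at 0.5 to 2 per 100 person-years, and 7 to 14% at 5 to 10. A true ratio of 2.0 reads 1.985 to 1.942 across the lower range of SoC rates. The higher rates are illustrations and find no support in the documents. The direction of the ratio error cannot be assumed when follow-up differs between cohorts.

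This is a minor inconsistency that should be corrected. It does not threaten the study's conclusions.

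**What to change.** In SAP section 7.9.4.5:

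1. Define the incidence-rate denominator as days from index to the first event or censoring, whichever is earlier, to match protocol section 10.3.7.5.
2. Keep total follow-up days for recurrent-event rates only.
3. Reconcile the statements that each event gets an incidence rate (protocol 10.3.7.5 and SAP 7.9.4.5) with the SAP's restriction to once-only events, by naming the outcomes that receive each type of rate.

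The cost is one phrase and a short list of outcomes. No new data should be needed beyond event dates, and the edit can be made when the SAP is finalized before the first data cut.
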